8.7.3 Clinical Laboratory Tests

8.7.3.1 Serum Chemistry, Hematology, Urinalysis, Pregnancy Tests

Laboratory safety variables include hematology, clinical chemistry and urinalysis panels. The complete list of laboratory tests is included in Table 4 below.

Table 4. Clinical Laboratory Tests

Serum Chemistry (Units)	Hematology (Units)	Urinalysis
ALT (IU/L)	Basophils (109/L)	Appearance
AST (IU/L)	Basophils/Leukocytes (%)	Bilirubin
Albumin (g/L)	Eosinophils (109/L)	Color
Alkaline Phosphatase (IU/L)	Eosinophils/Leukocytes (%)	Glucose
Total Bilirubin (umol/L)	Mean cell hemoglobin (MCH)	Ketones
Direct Bilirubin (umol/L)	Mean Corpuscular HGB Concentration	Leukocyte Esterase
Calcium (mmol/L)	(g/L)	Nitrite
Carbon Dioxide (mmol/L)	Mean Corpuscular Hemoglobin (fmol)	Occult Blood
Chloride (mmol/L)	Mean Corpuscular Volume (fL)	pH
Creatinine (umol/L)	Hematocrit (%)	Protein
Glucose (mmol/L)	Hemoglobin (g/L)	Specific Gravity
Magnesium (mmol/L)	Lymphocytes (109/L)	Urobilinogen
Phosphorus (mmol/L)	Lymphocytes/Leukocytes (%)	
Potassium (mmol/L)	Monocytes (109/L)	Urine Microscopic
Total Protein (g/L)	Monocytes/Leukocytes (%)	
Sodium (mmol/L)	Neutrophils (109/L)	Urine pregnancy
Urea Nitrogen (mmol/L)	Neutrophils/Leukocytes (%)	test
	Platelets (109/L)	
	Red Blood Cell Count (1012/L)	

	White Blood Cell Count (109/L)	
--	--------------------------------	--

Clinical laboratory parameters will be obtained at times indicated in the SoA in Appendix 11.1. Cutoff values considered to be potentially clinically important (PCI) for selected laboratory tests are outlined in Appendix 11.2.

A summary of subjects meeting any of the PCI criteria for post-baseline laboratory measurements will be provided by treatment group. All clinical laboratory test results will be provided in data listings with PCI criteria flagged.

Separate data listings for urine and serum pregnancy tests will be provided in female subjects of childbearing potential.

Potential Hy's law (ALT or AST > 3 x ULN concurrent with total bilirubin > 2 x ULN at the same visit) will be summarized by treatment group and listed. eDish plots will be used to present subjects potentially meeting Hy's law.

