PRV-015, a fully human immunoglobulin (IgG1κ) mAb, binds to and inhibits the function of IL-15 in all of its presentations (cis, trans, soluble IL-15 bound to IL-15R α), and blocks IL-15-induced T-cell proliferation (Villadsen 2003). It has also demonstrated dose-dependent inhibition of IL-15-induced tumor necrosis factor alpha (TNF- α) production. Thus, PRV-015 is a plausible candidate for the treatment of celiac disease.

PRV-015 was previously tested in clinical trials for efficacy and safety in patients with rheumatoid arthritis (RA) (Baslund 2005, McInnes 2006), refractory celiac disease Type II (RCD-II) (Cellier 2019), and psoriasis (Lebrec 2013) and has shown acceptable safety and tolerability in all studies. Proof of concept was achieved in RA and RCD-II, while PRV-015 showed no efficacy in psoriasis.

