9.4.5. Safety Analyses

The Safety population will be used for all safety analyses. The safety variables, including AEs (coded using the Medical Dictionary for Regulatory Activities [MedDRA]) will be tabulated by actual treatment received. TEAEs, TEAEs leading to withdrawal, treatment-emergent SAEs, and AESIs will be tabulated by MedDRA system organ class and preferred term. PCI laboratory tests and vital signs will be tabulated and listed by visit. Additionally, AEs and SAEs will be tabulated separately for subjects enrolled in the 4-week placebo run-in period.

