11.2 PCI criteria for Hematology, Serum Chemistry, Urinalysis

		C	conventional Uni	its	SI Units					
Test Name	Sex	Reference Range	Units	PCI Criteria	Reference Range	Units	PCI Criteria			
Hematology			1							
	М	13.5 – 17.5	g/dL	< 8.1 or > 20	135 - 175	g/L	< 81 or > 200			
Hemoglobin	F	12.0 – 15.5	g/dL	< 8.1 or > 20	120 - 155	g/L	< 81 or > 200			
Hemoglobin				2 point decrease from baseline			20 point decrease from baseline			
White Cell Count		4.0 – 11.0	x10E3/uL	< 2.1 or > 35	4.0 - 11.0	x10E9/L	< 2.1 or > 35			
Eosinophils (Abs)		0.0 - 0.6	x10E3/uL	>=3	0.0 - 0.6	x10E9/L	>=3			
Neutrophils (Abs)		1.5 - 7.7	x10E3/uL	<1	1.5 - 7.7	x10E9/L	<1			
Platelets	17	150 - 450	x10E3/uL	< 100 or > 1000	150 - 450	x10E9/L	< 100 or > 1000			
Serum Chemistry										
	М	5.9 - 8.0	g/dL	< 4.0	59 – 80	g/L	< 40			
Protein (Total)	F	6.2 - 7.9	g/dL	< 4.0	62 - 79	g/L	< 40			
	М	4.03 - 5.51	g/dL	< 2.0	40.3 – 55.1	g/L	< 20			
Albumin	F	4.02 - 5.24	g/dL	< 2.0	40.2 - 52.4	g/L	< 20			
	М	6.7 – 33.4	IU/L	>=3X ULN	6.7 – 33.4	IU/L	>=3X ULN			
ALT	F	6.6 - 22.9	IU/L	>=3X ULN	6.6 - 22.9	IU/L	>=3X ULN			
	М	12.4 – 33.0	IU/L	>= 3X ULN	12.4 – 33.0	IU/L	>= 3X ULN			
AST	F	11.8 – 25.7	IU/L	>= 3X ULN	11.8 – 25.7	IU/L	>= 3X ULN			
	М	36.1 – 124.2	ĮU/L	>= 3XULN	36.1 – 124.2	IU/L	>= 3XULN			
AP (AlkPhos)	F	35.6 - 118.3	ĮU/L	>= 3XULN	35.6 - 118.3	IU/L	>= 3XULN			
	М	0.24 - 1.49	mg/dL	>=2X ULN	4.10 - 25.48	umol/L	>=2X ULN			
Bilirubin (Total)	F	0.19 - 1.13	mg/dL	>=2X ULN	3.25 - 19.32	umol/L	>=2X ULN			

			Conventional Ur	nits		SI Units	
Test Name	Sex	Reference Range	Units	PCI Criteria	Reference Range	Units	PCI Criteria
	М	20 - 32	mmol/L	< 18 or > 40	20 - 32	mmol/L	< 18 or > 40
Bicarbonate	F	19 - 29	mmol/L	< 18 or > 40	19 - 29	mmol/L	< 18 or > 40
	М	8.2 - 23.8	mg/dL	> 40	2.93 - 8.50	mmol/L	>14.25
BUN (Urea)	F	5.9 - 21.4	mg/dL	> 40	2.11 - 7.64	mmol/L	>14.25
	М	8.5 - 10.3	mg/dL	< 6 or > 12	2.13 - 2.58	mmol/L	< 1.5 or > 3
Calcium	F	8.5 – 10.2	mg/dL	< 6 or > 12	2.13 – 2.55	mmol/L	< 1.5 or >
	М	98 – 108	mmol/L	< 90 or > 125	90 – 108	mmol/L	< 90 or > 125
Chloride	F	99 - 107	Mmol/L	< 90 or > 125	99 - 107	mmol/L	< 90 or > 125
	М	0.63 - 1.20	mg/dL	>=1.5	55.69 - 106.08	umol/L	>=132
Creatinine	F	0.51 - 0.96	mg/dL	>=1.5	45.08 - 84.86	umol/L	>=132
Glucose		< 140	mg/dL	> 500	< 7.8	mmol/L	> 27.75
	М	1.8 – 2.2	mg/dL	<1.22 or >4.87	0.74-0.90	mmol/L	<0.5 or >2
Magnesium	F	1.7 – 2.2	mg/dL	<1.22 or >4.87	0.70 - 0.90	mmol/L	<0.5 or >2
	М	2.1 - 4.6	mg/dL	< 0.5	0.68 - 1.49	mmol/L	< 0.5

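### The SAP specifies no by-arm summary of lymphocyte values and no lymphocyte PCI criterion, so the planned laboratory tables could not detect or exclude a dose-related lymphocyte shift

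*SAP*

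**What the plan says.** SAP Table 4 includes lymphocytes both as an absolute count and as a percentage of leukocytes. For the safety laboratory panels, SAP 8.7.3.1 then specifies the following.

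- A PCI summary by arm: "A summary of subjects meeting any of the PCI criteria for post-baseline laboratory measurements will be provided by treatment group".
- Listings: "All clinical laboratory test results will be provided in data listings with PCI criteria flagged".
- Potential Hy's law (ALT or AST above three times ULN, "concurrent with total bilirubin > 2 x ULN at the same visit) will be summarized by treatment group and listed", with eDish plots.

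PCI limits exist for only part of Table 4: "Cutoff values considered to be potentially clinically important (PCI) for selected laboratory tests are outlined in Appendix 11.2". The hematology rows of that appendix are hemoglobin, white cells, eosinophils, neutrophils and platelets. The row that comes nearest to lymphocytes is "White Cell Count", flagged below 2.1 or above 35 x10⁹/L.

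For vital signs and weight (SAP 8.7.4.1 and 8.7.4.2), descriptive statistics by visit and treatment group are promised. SAP 8.7.3.1 has no matching sentence for hematology or chemistry. The protocol's safety analysis section (9.4.5) is also framed in PCI terms: "PCI laboratory tests and vital signs will be tabulated and listed by visit".

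**The concern.** Protocol 2.2 describes a drug that "blocks IL-15-induced T-cell proliferation", and severe opportunistic infection is an adverse event of special interest. Protocol 4.2 says the trial compares three doses with placebo in order to select one or more for further development. A peripheral lymphocyte count is a natural laboratory measure to compare across those doses, and it is already being collected.

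Under the outputs as written, no table sets lymphocyte values side by side by arm. If the counts fell modestly and in step with dose, each result might look unremarkable to the investigator who reviewed it, and the pattern would lie scattered through subject listings. A study report could then state that no laboratory signal was seen when the tables were not built to show this one.

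**Working it through.** The plan states no figure to reproduce here. The check compares what is measured with what is tabulated, and then asks whether the white cell criterion can stand in for a lymphocyte criterion.

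**Step 1: routes to a by-arm table.**
- Lymphocyte PCI count: none, because Appendix 11.2 has no lymphocyte row.
- Descriptive statistics or shift table for lymphocytes: none specified in SAP 8.7.3.1.
- Hy's law summary: by arm, but uses only transaminases and bilirubin.
- Adverse events: available if an investigator judges the change clinically relevant (Protocol 8.3.4, 10.2.1). It then enters the by-arm tables of treatment-emergent events (SAP 8.7.2).
- White cell PCI: available if the total falls below 2.1.

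**Step 2: can the white cell limit act as a proxy?** Let W be the baseline white cell count and L the baseline lymphocyte count, both x10⁹/L. Assume other leukocytes stay constant. If all lymphocytes are lost, the count becomes W − L, and the flag requires W − L < 2.1. Equivalently, the lymphocyte share must satisfy L/W > 1 − 2.1/W.

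| W | Where it comes from | Share needed, 1 − 2.1/W |
|---|---|---|
| 3.0 | entry minimum, Protocol 5.2 | 30% |
| 4.0 | lower reference limit, SAP 11.2 | 47.5% |
| 5.0 | illustration | 58% |
| 6.0 | illustration | 65% |
| 7.0 | illustration | 70% |

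Anyone with W − L of at least 2.1 cannot be flagged through lymphocyte loss, however complete.

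**Step 3: worked cases.** The documents give no baseline lymphocyte counts, so those below are assumed (range 1.5 to 3.0).
- W 6.0, L 2.0, total loss: 6.0 − 2.0 = 4.0. No flag, and still within the 4.0–11.0 reference range.
- W 5.0, L 1.5, total loss: 3.5. No flag.
- W 4.0, L 1.5, total loss: 2.5. No flag.
- W 4.0, L 2.0, 90% loss: 4.0 − 1.8 = 2.2, no flag. Total loss: 2.0, flagged.
- W 3.0, L 1.5, 50% loss: 2.25, no flag. 90% loss: 3.0 − 1.35 = 1.65, flagged.
- W 5.0, L 3.0, total loss: 2.0, flagged.

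The proxy works only at a low white cell count or a high lymphocyte share.

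**Step 4: how much data is involved.** The schedule has seven post-baseline visits with clinical laboratory samples (Visits 5, 7, 9, 11, 13, 15 and 16). With about 220 subjects and full attendance, 220 × 7 = 1,540 absolute lymphocyte values are collected, for which SAP 8.7.3.1 names no output other than a listing.

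**Step 5: what a by-arm table would offer.** With 55 per arm, two-sided 0.05 and 80% power, the detectable mean difference between one dose and placebo is (1.960 + 0.842) × √(2/55) = 0.53 SD. A lymphocyte PCI count alone would be less sensitive. At assumed rates of 2% on placebo against 10%, 15% or 20% on a dose, power is about 42%, 69% or 87%. The descriptive table therefore matters more than the added criterion.

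**The case against.** The strongest reply is that the protocol's laboratory endpoint is PCI change, the SAP delivers it, and choosing which analytes carry a limit is a legitimate decision. That is right as far as it goes: nothing here contradicts the protocol.

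The plan also hints that laboratory summaries were in mind. SAP 8.2.3 sets rules for values outside the quantitation limits for use in summary statistics on all clinical laboratory assessments. SAP 8.2.1 gives default statistics for continuous variables. These hints make the gap look like under-specification rather than a decision to rely on listings, but neither creates a lymphocyte table.

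Three stronger readings are tempting, and the documents do not support them.

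- A reader might infer that laboratory safety is summarised by arm through PCI counts alone. Hy's law is also summarised by arm, although it carries no lymphocyte information.
- A reader might infer that depletion in every subject could pass without trace in any by-arm table. A clinically significant abnormal result meets the adverse event definition and would enter the event tables, and some subjects with few other leukocytes would meet the white cell criterion. What remains exposed is a fall that investigators do not report.
- A reader might infer that the protocol's by-visit PCI tabulation was dropped without being recorded in SAP 8.10. SAP 8.2 has a general rule that outputs are by treatment and visit where applicable, and SAP 8.2.2.2 says by-visit analyses use nominal time points. The missing words in 8.7.3.1 are at most an ambiguity.

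It is also fair to say that lymphocyte depletion is an inference from mechanism. Protocol 2.3, after more than 250 exposed subjects, lists injection site reaction, infusion site pain, rash and eczema as identified reactions, and no lymphopenia. Opportunistic infections are tabulated by arm with risk differences, and the monitoring committee receives unblinded data. These lower the stakes, but they do not give the study report a comparison of lymphocyte values between doses.

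**Conclusion.** The point holds in a limited form. Lymphocytes are measured, but no by-arm summary of their values and no PCI criterion for them is specified. A fall reaches a by-arm table only through an investigator's adverse event report or a white cell count below 2.1 x10⁹/L. The second route needs a lymphocyte share above 30% at a white cell count of 3.0, rising to 65% at 6.0, even if every lymphocyte is lost. This arithmetic assumes that other leukocytes do not change; the worked cases also rest on assumed baseline counts.

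The conclusion does not say that lymphopenia is expected or has occurred. It says that in a dose-selection trial of a drug with this mechanism, the planned tables could neither show nor rule out a dose-related shift. No data are lost, since every value is listed and a table could be made later. However, a table requested after unblinding carries less weight than one specified beforehand. This is a worthwhile, low-cost improvement, not a threat to the trial's main conclusions.

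**What to change.** In SAP 8.7.3.1, add descriptive statistics of observed value and change from baseline, by visit and treatment group, for absolute lymphocytes and the other continuous hematology and chemistry tests in Table 4. This gives the quantitation-limit rule in SAP 8.2.3 a table to apply to.

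In Appendix 11.2, add a row for absolute lymphocytes, with a cut-off chosen by the sponsor and fixed before unblinding.

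It would also help to write by visit into the PCI summary sentence, so that it matches Protocol 9.4.5 without relying on the general rule in SAP 8.2.

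The cost is a few more standard tables and one appendix row. No new data, visits or samples are needed.

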3.2 Secondary Objectives and Endpoints

The secondary objectives are:

- To assess the effect of treatment with PRV-015 on other measures of disease activity.
- To assess the safety, tolerability, and pharmacokinetics (PK) of PRV-015 when administered to adult patients with NRCD.

The secondary efficacy endpoints are:

- Absolute change from baseline through Week 24 in the Diarrhea and Loose Stool domain of the CeD PRO.
- Absolute change from baseline through Week 24 in gastrointestinal (GI) symptoms as assessed by the Total GI score (comprising the Abdominal Symptoms domain, the Diarrhea and Loose Stool domain, and the Nausea item) of the CeD PRO.
- Absolute change from baseline to Week 24 in small intestinal mucosal inflammation, as measured by intraepithelial lymphocyte (IEL) density using immunohistochemistry (IHC).

Confidential Page

The secondary safety endpoints are:

- Adverse events (AEs): treatment-emergent adverse events (TEAEs), TEAEs leading to treatment discontinuation, and treatment-emergent serious adverse events (SAEs).
- Treatment-emergent adverse events of special interest (AESIs).
- Potentially clinically important (PCI) changes in clinical laboratory values (hematology, chemistry, and urinalysis), vital signs (blood pressure [BP], heart rate, temperature, respiratory rate) and weight.
- Immunogenicity, as assessed by the presence of anti-PRV-015 antibodies.

[figure not shown]
The secondary PK endpoint is:

Serum PRV-015 trough concentrations (C_{min}).

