Symptomatic days will be assessed in terms of the Abdominal Domain, Diarrhea and Loose Stool Domain, and Total GI score of the CeD PRO. A given day is defined as a symptomatic day if any of the domain scores is >0. A day is considered asymptomatic if all of these scores are 0. The number of symptomatic days and asymptomatic days will be derived by month (including baseline) [based on month-based visit windows defined below] and total during the double-blind treatment period (through Week 24).

Weekly Worst Symptom Domain Score in CeD PRO

Weekly worst symptom domain scores will be derived separately for each of the following three domains: 1) Abdominal Domain score, 2) Diarrhea and Loose Stool Domain score, and 3) Total GI score by selecting the worst daily score for all items within each domain for a given week (based on analysis visit windows defined below) and averaging these scores.

BSFS Stools of Type 6 or 7

The BSFS is a pictorial aid to help subjects identify the shape and consistency of their stools during the study (Riegler et al, 2001). The subject will be asked to record the number of stools that have a consistency of Type 6 or 7 (loose stool or entirely liquid) at bedtime daily in the eDiary. On the days in which the subject experiences no such stool (BSFS Type 6 or 7), the subject should record 0 in the eDiary instead of leaving it blank. The sum of weekly stool frequency (sum of the previous 7 days) through Week 24 for stools of BSFS Type 6 or 7 will be calculated, based on the analysis visit windows (defined below). In case of multiple records for stool in one day the latest record in time will be considered.

Baseline Value for Patient-Reported Assessments captured in eDiary

In general, the last non-missing value prior to the first dose of double-blind treatment will be used as the baseline value.

For patient-reported assessments captured in the eDiary, the following definitions of baseline in Table 2 will be used:

Table 2. Definition of Baseline for Patient-Reported Assessments Captured in eDiary

Assessment	Baseline Definition				
CeD PRO (Abdominal domain and other weekly domain scores)	Average of scores from 7 days prior to randomization (e.g., last week of placebo run-in).				
BSFS	Sum of Type 6 or 7 stool experienced over the 7 days prior to the date of first dose of double-blind treatment.				
PGIC/PGIS	Most recent assessment prior to the first administration of double-blind treatment.				

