11.3 PCI criteria for Vital Signs and Weight

Vital signs		
HR	≤50 bpm and decrease from baseline ≥20 bpm	
	≥120 bpm and increase from baseline≥20 bpm	
SBP	≤95 mmHg and decrease from baseline ≥20mmHg	
	≥160 mmHg and increase from baseline ≥20 mmHg	
DBP	≤45 mmHg and decrease from baseline ≥10 mmHg	
	≥110 mmHg and increase from baseline ≥10 mmHg	

Weight	≥5% increase from baseline	FDA Feb 2007	
	≥5% decrease from baseline		

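### The laboratory PCI table counts pre-existing abnormalities that persist as if they were PCI changes, because all but one criterion has no baseline condition (minor)

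*SAP*

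**What the plan says.** SAP 3.2 lists among the secondary safety endpoints "Potentially clinically important (PCI) changes in clinical laboratory values (hematology, chemistry, and urinalysis"), together with vital signs and weight. The Protocol's objectives table has the same endpoint.

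For laboratory values, SAP 8.7.3.1 first points to the limits: "Cutoff values considered to be potentially clinically important (PCI) for selected laboratory tests are outlined in Appendix 11.2". It then gives the counting rule: "A summary of subjects meeting any of the PCI criteria for post-baseline laboratory measurements will be provided by treatment group". All results are also listed with PCI values flagged, and potential Hy's law cases are summarized, listed and plotted. No laboratory shift table or treatment-emergent PCI definition is planned.

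In Appendix 11.2 one laboratory criterion refers to baseline, for hemoglobin: "2 point decrease from baseline" (20 points in SI units). The other criteria are absolute levels or grades. In Appendix 11.3 each vital-sign criterion joins a level to a change, for example "≤50 bpm and decrease from baseline ≥20 bpm", and weight is judged on change alone, for example "≥5% increase from baseline".

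A general baseline rule appears in SAP 8.2.2.1: "In general, the last non-missing value prior to the first dose of double-blind treatment will be used as the baseline value". It stands in the section on eDiary assessments and is not repeated for laboratory tests.

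**The concern.** The endpoint speaks of changes, but the planned count for nearly all laboratory tests is of levels. A stable abnormality that was present before the first double-blind dose enters the by-arm table in the same way as one that arose on treatment. This departs from the SAP's approach elsewhere: Appendix 11.3 requires change, and SAP 8.7.2 reports screening and run-in adverse events separately from treatment-emergent ones. SAP 8.10 gives no reason for treating laboratory values differently.

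Apart from the Hy's law output, this is the only by-arm laboratory summary that 8.7.3.1 specifies for these panels. In a trial meant to inform dose selection, with about 55 subjects per arm, carried-over subjects make a real difference between arms look smaller in relative terms. A chance imbalance in pre-existing findings could also pass for a drug effect.

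**Working it through.** The documents state no figure for the PCI analysis, so there is none to reproduce. The check has four parts.

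**1. Which criteria use baseline (SAP Appendices 11.2 and 11.3)**

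| Group | Criteria that use baseline |
|---|---|
| Laboratory (11.2) | One: the 2-point hemoglobin decrease |
| Vital signs (11.3) | All six |
| Weight (11.3) | Both |

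**2. What entry criteria already guard (Protocol 5.2, exclusion 5, against Appendix 11.2)**

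| Test | Excluded at entry | PCI limit |
|---|---|---|
| Hemoglobin (low) | <9 g/dL | <8.1 g/dL |
| White cells (low) | <3,000/mm³ | <2.1 ×10³/µL |
| Platelets (low) | <100,000/mm³ | <100 ×10³/µL |
| Creatinine | >1.5 mg/dL | ≥1.5 mg/dL |
| ALT and AST | >3 × ULN | ≥3 × ULN |
| Bilirubin, alkaline phosphatase, neutrophils, eosinophils, electrolytes, albumin, urinalysis | no limit | limits set for most items |

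The guard is incomplete. It names screening or Visit 1, whereas laboratory samples are also taken at Visit 3. The transaminase exclusion is worded with a conjunction (ALT and AST), so read literally an isolated elevation could enter. Still, it covers most of the main hematology, liver-enzyme and renal limits. Among the unguarded tests several PCI limits are extreme (eosinophils ≥3 against an upper reference limit of 0.6; sodium <125 or >160 mmol/L), so a baseline value beyond them should be rare. Some urinalysis limits lie close to the reference range: hyaline casts >1 against 0–1, and urine white cells ≥10 against 0–5 per high-power field.

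**3. Expected carry-over with no drug effect**

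Inputs from the documents: about 55 subjects per arm (SAP 7) and seven post-baseline laboratory visits (5, 7, 9, 11, 13, 15 and 16; SAP Appendix 11.1). Assumed: prevalence p of one flag at any visit of 1% to 5%, and an equicorrelated latent normal with within-subject correlation ρ.

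Carried-over subjects per arm = 55 × p × P(flag at one or more of seven visits | flag at baseline).

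| ρ | p | P(counted given baseline flag) | Share of counted subjects flagged at baseline | Carried over per arm |
|---|---|---|---|---|
| 0.3 | 1% | 28% | 5% | 0.15 |
| 0.3 | 5% | 55% | 11% | 1.5 |
| 0.6 | 1% | 57% | 12% | 0.3 |
| 0.6 | 5% | 75% | 21% | 2.1 |
| 0.8 | 1% | 77% | 23% | 0.4 |
| 0.8 | 5% | 86% | 32% | 2.4 |

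For example, 55 × 0.01 × 0.57 = 0.31 and 55 × 0.05 × 0.86 = 2.4. These are per criterion. The SAP does not say whether the table has one row per criterion or a single any-criterion row; in a single row, carry-over would accumulate across criteria.

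**4. Dilution and chance imbalance**

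Let b be the share beyond a limit at baseline, all persisting (the worst case), and r the rate of new PCI values. The counted rate is b + (1 − b) × r. Assume r = 5% on placebo and 20% on one dose, a true risk ratio of 4.0.

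- b = 2%: 0.02 + 0.98 × 0.05 = 6.9% against 0.02 + 0.98 × 0.20 = 21.6%; ratio 3.1.
- b = 10%: 0.10 + 0.90 × 0.05 = 14.5% against 0.10 + 0.90 × 0.20 = 28.0%; ratio 1.9.

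Counting only subjects not beyond the limit at baseline returns 5% against 20%, ratio 4.0.

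For chance imbalance, treat the number with a baseline flag in each arm as binomial (55, b). Two arms differ by three or more such subjects with probability 27% at b = 5% and 42% at b = 10%.

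**The case against.** The case for leaving the plan alone has real weight.

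- The table is descriptive. SAP 8.7.3.1 plans no test or interval on PCI counts, so no formal inference is damaged. This stands.
- Randomization spreads pre-existing abnormalities evenly in expectation. A reader might infer that the rule biases the comparison for or against active drug; the design gives no ground for that.
- A reader might also infer that baseline is ignored altogether, or that a subject flagged at baseline is counted whatever happens on treatment. Neither holds. Hemoglobin has a change criterion, and a subject whose later values all return within the limit is not counted. In the grid above, 14% to 43% of baseline-flagged subjects are never counted at correlation 0.6 to 0.8.
- Exclusion 5 covers the main hematology, liver-enzyme and renal limits, and exclusion 11 lets the investigator exclude clinically significant disease. This narrows the problem but does not close it, least of all for urinalysis.
- The flagged listings, the Hy's law output and the investigator's duty to judge whether a laboratory change is an adverse event (Protocol 8.3.4) limit misreading. They do not correct the by-arm count.
- The contrast with Appendix 11.3 is one of definitions. SAP 8.7.4.1 plans only a listing for vital-sign PCI values, so no parallel SAP count exists.
- Replacing the present count with one limited to subjects not flagged at baseline could hide harm: someone at 2 × ULN bilirubin who rises to 6 × ULN would drop out of numerator and denominator. This is right, and it shapes the fix.

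**Conclusion.** The point holds as a minor one. As written, the laboratory PCI count mixes new abnormalities with pre-existing ones that persist, and so does not match an endpoint worded as changes. The exposure is mainly in tests without an entry limit, chiefly urinalysis and perhaps bilirubin.

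The consequence is dilution of between-arm contrasts and some chance imbalance in a descriptive table. On the assumed 1% to 5% prevalence and correlation 0.6 to 0.8, that is about 0.3 to 2.4 carried-over subjects per arm per criterion, or 12% to 32% of those counted. These assumptions have no source in the documents. For the tests with extreme limits the true prevalence may be well below 1%; for some urinalysis items it could be higher. The documents do not support calling this a serious defect of the safety analysis.

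**What to change.** In SAP 8.7.3.1:

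1. Keep the present count and the flagged listings.
2. Add, for each parameter and arm, the number of subjects who meet the PCI criterion after baseline but did not meet it at baseline, with subjects not meeting it at baseline as the denominator.
3. Add a shift table from baseline to worst post-baseline value, so that worsening in subjects already beyond a limit remains visible.
4. State that the laboratory baseline is the last non-missing value before the first double-blind dose, in line with the general rule in 8.2.2.1.

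The cost is one or two extra tables and slightly smaller denominators for the added count. No new data are needed.
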